### 5.9.2. Primary Efficacy Endpoint Analysis

#### 5.9.2.1. MITT Population Analysis

Data will be analyzed based on the E-MITTv5 population (see Section 3.1.1) using a restricted maximum likelihood-based (REML) MMRM, including a nominal visit variable, the treatment indicator and the interaction term between treatment and visit, the randomization stratification variables (see Section 2.6) as fixed factors, and the respective efficacy Baseline value as covariate; with an unstructured covariance matrix and the Kenward and Roger method of calculating the denominator degrees of freedom for the tests of fixed effects.

Sample SAS code (will be fully validated at the analysis stage):

```

PROC MIXED DATA=dataset METHOD=REML COVTEST;
  CLASS subject treatment(REF='Control') visit severity(REF='moderate') region(REF='Europe')
  prioruse(REF='None');
  MODEL scorediff = treatment/visit severity region prioruse scorebl / SOLUTION CL
  DDFM=KENWARDROGER;
  REPEATED visit / SUB=subject TYPE=UN;
  LSMEANS treatment*visit visit / CL;
  *BY_IMPUTATION_;
  LSMESTIMATE treatment*visit "intervention effect at Week 52" 0 0 0 1 0 0 0 -1 / CL;
  *Summary statistics for treatment difference based on LSM
  LSMESTIMATE treatment*visit "intervention effect at Week 13" 1 0 0 0 -1 0 0 0 / CL;
  LSMESTIMATE treatment*visit "intervention effect at Week 26" 0 1 0 0 0 -1 0 0 / CL;

```

Sponsor:	TauRx Therapeutics Ltd.		
Protocol:	TRx-237-039		
Document Version No.:	3.0	Document Date:	07-JUN-2023

*LSMESTIMATE treatment\*visit "intervention effect at Week 39" 0 0 1 0 0 0 -1 0 / CL;  
RUN;*

If the mixed model does not converge, the unstructured covariance matrix is replaced by firstly, an auto-regressive covariance structure then by a compound symmetry covariance structure. If the model still does not converge, the randomization stratification variables will be removed, in the following order: region, prior AChEI and/or memantine use, MMSE.

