## 17 STATISTICAL ANALYSIS

A SAP will be finalized and signed off prior to database lock and unblinding. The SAP will provide details about the planned analysis. A brief overview of the plans for the primary analysis and selected secondary and exploratory analyses is given in the following sections. Specific ROI and SPM techniques and comparisons to previous Phase 3 data or external databases as well as Population PK analyses will be described in the SAP or a corresponding additional SAP where necessary; the SAP will provide details.

Changes to the planned analysis will be documented in the SAP prior to database lock and unblinding. Deviations from the SAP (if any) will be noted in the clinical study report.

The primary target of estimation is the difference in ADAS-cog11 and ADCS-ADL23 over 52 weeks in subjects receiving the LMTM dose of 16 mg/day as compared to placebo.

The primary efficacy analyses for FDA will be performed on the Efficacy Modified Intent-to-Treat (E-MITT) which will include all randomized subjects who took at least one dose of study drug and have a baseline and a valid post-baseline efficacy assessment, and for EMA on the Intent-to-Treat (ITT) population with conservative assumptions about disease progression made for subjects who have missing post-baseline assessments. Subjects will be analyzed in the treatment group and according to the stratification variables to which they were randomized.

Changes from baseline to Week 52 on the co-primary efficacy endpoints and other modalities with repeated measures such as MRI will be analyzed using a linear mixed model for repeated measures with unstructured covariance matrix (this assumption about the covariance matrix might be relaxed if the model does not converge; the SAP will provide details). The linear mixed model will contain fixed effects for time, treatment, and a treatment-by-time interaction; additionally, the baseline value of the corresponding endpoint will be included as a covariate and the randomization stratification variables of prior usage of AChEIs and/or

memantine, MMSE split (16-19, 20-25 or 26-27) as determined at Screening, and region will be included as fixed effects in the model. F-FDG-PET and other modalities with only one planned post-baseline assessment will be analyzed using an ANCOVA; the covariates for this model will be adjusted accordingly by removing terms with time.

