### 5.1. Primary Efficacy Analysis

There are two co-primary efficacy endpoints for this trial: Baseline adjusted decline in ADAS-cog11 and Baseline adjusted decline in ADCS-ADL23 from Baseline at Week 52. Repeated measurements on these endpoints scheduled at Weeks 13, 26, 39, and 52 will be treated using a mixed effects model (see Section 5.9). Suppose  $\mu_{ADAS-cog11,T}$  and  $\mu_{ADCS-ADL23,T}$  are the means of decline at Week 52 for the treated arm and  $\mu_{ADAS-cog11,C}$  and  $\mu_{ADCS-ADL23,C}$  are the corresponding means for the control arm, then the global null and the alternative primary efficacy hypotheses can be written as:

$H_0: \mu_{ADAS-cog11,T} = \mu_{ADAS-cog11,C}$  OR  $\mu_{ADCS-ADL23,T} = \mu_{ADCS-ADL23,C}$  ; versus

$H_1: \mu_{ADAS-cog11,T} \neq \mu_{ADAS-cog11,C}$  AND  $\mu_{ADCS-ADL23,T} \neq \mu_{ADCS-ADL23,C}$  .

Thus, the global null versus alternative is a Union-Intersection Test (UIT) which requires both co-primary endpoints to meet statistical significance at the 5% two-sided level of significance for the global null hypothesis to be rejected.

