### 5.2. Multiple Comparisons/Multiplicity

In the double-blind treatment phase, the primary comparison is between HMTM 16 mg/day and control, based on subjects randomized under study protocol version 5.0 or higher.

Both co-primary endpoints must reach significance based on the use of a two-sided test at the alpha=0.05 level of significance for HMTM 16 mg/day to be designated as superior to control. This is because the global null hypothesis is only rejected if and only if the null hypothesis for each of the two co-primary endpoints are rejected. Furthermore, since the efficacy endpoints are primarily analyzed based on two different analysis populations (ITTv5, and the respective MITTv5), the pre-defined sequence is MITTv5 before ITTv5. ITT and MITT populations will be analyzed in the framework of sensitivity analyses.

Therefore, no multiplicity adjustment is necessary.

Sponsor:	TauRx Therapeutics Ltd.		
Protocol:	TRx-237-039		
Document Version No.:	3.0	Document Date:	07-JUN-2023

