### 5.3. Sample Size Justification

Sample size estimations to achieve 90% power (two-sided alpha = 0.05) to detect a difference between HMTM 16 mg/day and true placebo have been performed for the two co-primary clinical endpoints. These assume a withdrawal rate of 20% to 25% over 52 weeks. The study sample size – here restricted to subjects randomized under protocol version 5.0 or higher as this is the primary analysis population – of approximately 450 subjects (approximately 200 subjects in each treatment group, with a further 50 subjects for secondary analyses of an HMTM 8 mg/day group) is based on the ADCS-ADL23 as a larger sample size is required to achieve the target power.

Based on an estimated decline in ADCS-ADL23 over 52 weeks in the control arm of 7.7 units with an estimated SD of 8.5 units, the study will have approximately 93.2% power (two-sided alpha=0.05) to detect a reduction in decline of 3.4 units or more. The 3.4 units are motivated by an estimated treatment effect of  $5.0 \pm 1.6$  (mean  $\pm$  standard error) units in the pooled studies TRx-237-005/ TRx-237-015.

Based on an estimated decline in ADAS-cog11 over 52 weeks based on pooled information from Studies TRx-237-005 / TRx-237-015 in the control arm of 6.5 units with an estimated SD of 5.9 units, 200 subjects per treatment arm provide approximately 96.7% power (two-sided alpha=0.05) to detect a reduction in decline of 2.6 units or more. The 2.6 units represent a conservative value as the estimated treatment effect based on pooled Studies TRx-237-005 / TRx-237-015 is  $5.2 \pm 1.3$  (mean  $\pm$  standard error) units.

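### The covariance fallback for the MMRM names only structures that ordinarily assume equal variance at all visits; if it is used and variance grows to Week 52, per-endpoint type I error could be about 7-12%

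*SAP*

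**What the plan says.** SAP section 5.9.2.1 fits a REML repeated-measures model "with an unstructured covariance matrix and the Kenward and Roger method of calculating the denominator degrees of freedom for the tests of fixed effects". Section 5.1 gives the visits: "Repeated measurements on these endpoints scheduled at Weeks 13, 26, 39, and 52 will be treated using a mixed effects model".

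The fallback has one trigger: "If the mixed model does not converge". The order is then fixed: "the unstructured covariance matrix is replaced by firstly, an auto-regressive covariance structure then by a compound symmetry covariance structure". If that also fails, region, prior AChEI/memantine use and MMSE stratum are dropped in turn. The SAP does not say whether either replacement is the homogeneous or the heterogeneous version, and it names no robust standard error.

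Protocol section 17 leaves the matter to the SAP: "this assumption about the covariance matrix might be relaxed if the model does not converge; the SAP will provide details". The SAP sentence is therefore the only rule.

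On the success criterion, SAP section 5.2 says: "Both co-primary endpoints must reach significance based on the use of a two-sided test at the alpha=0.05 level of significance".

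**The concern.** Ordinary AR(1) and compound symmetry each have one variance and one correlation parameter. The four visits share the variance, and the Week 52 comparison is judged against the pooled value.

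In a progressive disease, subjects who decline at different rates spread apart over time, so the SD of change from baseline may well be larger at Week 52 than at Week 13. In that case the pooled variance is too small for Week 52, and the interval at the primary time point is too narrow. Kenward-Roger does not repair this, because it takes the fitted structure as correct.

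The same model is reused for the primary estimand (SAP 5.9.2.2), subgroups down to 10% of randomized subjects (5.9.2.1), the MRI models (5.9.3.1 and 5.9.3.3) and the 8 mg/day comparison (5.9.3.4).

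**Working it through.** **Inputs from the documents.** SAP 5.3 gives "approximately 200 subjects in each treatment group" and says "These assume a withdrawal rate of 20% to 25% over 52 weeks". It gives 52-week SDs of 8.5 (ADCS-ADL23) and 5.9 (ADAS-cog11), effects of 3.4 and 2.6 units, and power of 93.2% and 96.7%. Neither document gives an SD for Weeks 13, 26 or 39, or a between-visit correlation.

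**The plan's own figures.** With 25% withdrawal, n = 200 × 0.75 = 150 per arm.
- ADCS-ADL23: SE = 8.5 × √(2/150) = 0.981; 3.4/0.981 = 3.464; Φ(3.464 − 1.96) = 93.4%, or 93.2% with the t distribution.
- ADAS-cog11: SE = 5.9 × √(2/150) = 0.681; 2.6/0.681 = 3.816; Φ(3.816 − 1.96) = 96.8%, or 96.7% with t.

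Both stated powers reproduce. The plan states no type I error for the fallback, only the nominal 0.05.

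**Fallback, complete data.** A homogeneous structure estimates roughly the mean of the four visit variances. So

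SE ratio r = √(mean visit variance ÷ Week 52 variance), and type I error = 2 × Φ(−1.96 × r).

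The SD patterns below are assumptions, relative to Week 52 = 1. The last column allows for dropout. It takes the AR(1) or CS fit that maximises the expected likelihood and compares its model-based SE with the true SE, over four correlation patterns and 0-25% dropout.

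| SD at Weeks 13 / 26 / 39 | Mean variance | r | Error, complete data | Error, 0-25% dropout |
|---|---|---|---|---|
| 1.10 / 1.05 / 1.02 (falling) | 1.088 | 1.043 | 4.1% | 3.8-4.5% |
| 1 / 1 / 1 (flat) | 1 | 1 | 5.0% | 4.8-5.5% |
| 0.85 / 0.90 / 0.95 | 0.859 | 0.927 | 6.9% | 6.8-7.7% |
| 0.75 / 0.84 / 0.92 | 0.779 | 0.882 | 8.4% | 8.3-9.3% |
| 0.65 / 0.78 / 0.90 | 0.710 | 0.843 | 9.9% | 9.8-11.1% |
| 0.50 / 0.71 / 0.87 (variance proportional to time) | 0.625 | 0.791 | 12.1% | 12.1-13.7% |
| 0.25 / 0.50 / 0.75 (SD proportional to time) | 0.469 | 0.685 | 18.0% | 17-20% |

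REML simulation (3,000 trials per setting, about 194 per arm at the first visit, 22.5% dropout) gave 6.5% (AR) and 7.3% (CS) for the 0.85 pattern, and 10.3% and 10.4% for the 0.65 pattern. Monte Carlo error was 0.4-0.6 points.

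**Trial level.** Suppose each endpoint's error is 7-12%.
- Both endpoints null: both are significant in 0.5% to 4.9% of trials, for between-endpoint correlation 0 to 0.7.
- One null, the other with 93.2% power (taken as independent): 0.07 × 0.932 = 6.5% up to 0.12 × 0.932 = 11.2%.

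**Effect of the change.** With ARH(1) or CSH, the SE ratio was 1.00-1.01 and the error 4.8-4.9% in the three growing patterns run (0.85, 0.65, variance proportional to time), at 20% and 25% dropout and one correlation pattern. Heterogeneous Toeplitz was not run, but ARH(1) and CSH are special cases of it.

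**Covariance parameters for four visits.** Unstructured 10; heterogeneous Toeplitz 4 + 3 = 7; ARH(1) or CSH 4 + 1 = 5; AR(1) or CS 2. There is room between 10 and 2 to simplify the correlations while keeping a variance for each visit.

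**The case against.** **The trigger is unlikely.** The matrix is 4×4 and the primary comparison has about 400 randomized subjects. In simulated REML fits of the unstructured model (25% dropout), all 60 converged with 200 + 200 subjects, all 100 with 200 + 50, and all 300 with 40 subjects, about the size of a 10% subgroup. This was one covariance pattern and not the SAS procedure, so it does not rule out failure, but it gives no sign of a realistic one. This stands, and it sets the priority low. The smallest subgroups are where failure is somewhat more plausible, and the SAP already labels those analyses supplementary.

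**The plan does not say that variances are equal.** This is also correct. An auto-regressive structure could be ARH(1). Equal variance is the ordinary reading, not an explicit statement, so part of the defect is that the rule is incomplete: an analyst could choose the version after a fit has failed.

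**The protocol foresaw relaxing the matrix, and the SAP fixed an order in advance.** True, and a fixed order is good practice. It does not answer the point that both named structures, as ordinarily read, drop the feature that matters most for a Week 52 contrast.

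**The 8 mg/day comparison.** A reader might infer that its covariance matrix rests on 50 subjects. It does not. Protocol sections 17 and 17.4.2 use two treatment levels, so the 8 mg/day model pools about 50 + 200 = 250 randomized subjects.

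**Conclusion.** The point holds conditionally, as a minor improvement. If the fallback is used, if its structures are taken in their homogeneous form, and if variance grows to Week 52, then the Week 52 standard error is understated. Per-endpoint error is then about 7-12% for an assumed Week 13 to Week 52 SD ratio of about 0.85 to 0.5, and slightly above 12% at the lower end with dropout.

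Three stronger readings are not supported:
- *The SAP text alone implies 7-12%.* It does not. That range needs a variance-growth pattern that the documents do not give. A flat SD leaves the error near 5%, a falling SD takes it lower, and steeper growth takes it higher.
- *The trial's false-success rate is 7-12%.* The range is per endpoint. With both endpoints null, false success stays below 5% for the correlations examined (0 to 0.7). It reaches about 6.5-11.2% only when one endpoint is null and the other is effective.
- *The primary intervals are too narrow as planned.* The planned model is unstructured and does not have this problem. Nothing in the documents shows that the fallback was used.

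**What to change.** Replace the fallback sentence in SAP 5.9.2.1: on non-convergence use heterogeneous Toeplitz, then ARH(1), then CSH, before any homogeneous structure and before removing stratification factors; report the structure used for every model. Removing those factors can stay as a last step, since Protocol section 17.4 allows it when strata are sparse. Sandwich standard errors are optional: the heterogeneous structures alone restored about 5% in the cases run, and it would need to be said how a sandwich estimate fits with Kenward-Roger.

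The cost is one sentence and standard options in the same procedure. Timing matters, though. SAP section 10 records that version 3.0 followed the 28-APR-2022 snapshot and partial unblinding for the double-blind analysis. The rule for double-blind models already run should therefore not be rewritten as if pre-specified. Instead, state for each such model whether the fallback was used. If it never was, nothing more is needed. If it was, add a heterogeneous-structure rerun beside the original result, labelled post hoc.

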#### **Sensitivity analysis to the statistical model**

Model-based sensitivity analysis are:

- Including the interaction term Baseline\*visit (scorebl/\*visit) in model statement
- Maximum likelihood (ML) (rather than REML) based repeated measures model (*method=ml*) with polynomial (linear, quadratic, and cubic) time effects and time treated as a continuous variable (number of nominal weeks as well as actual study week defined by study day divided by 7). The estimated annualized change in mean values and standard errors from Baseline to Week 52 will be presented for each treatment group. For sample SAS code see Section 5.9.3.1.

#### **Supplementary and other sensitivity analyses**

Supplementary analyses are (starting population: E-MITTv5):

- Including subjects randomized before study protocol version 5.0 (E-MITT population)
- Restricted to the PP population
- Restricted to the completers (subjects who did not stop the study or the study medication early, during the double-blind treatment phase)
- Include assessments after initiation of an AChEI and/or memantine, if more than 5% of the randomized subjects initiated AChEI and/or memantine during the double-blind treatment phase
- Restricted to all visits not potentially confounded by intercurrent illnesses, COVID-19, and concomitant medications (which includes assessments after initiation of an AChEI and/or memantine) as identified during the BDRM
- Stratified by subgroups. If the subgroup consists of less than 10% of the randomized subjects, only summary statistics will be presented.
  - o AChEI/memantine use (prior use, never used) [binary]
  - o Verified AD diagnosis (probable AD, MCI-AD) [binary]
  - o MMSE (16-19, 20-25, and 26-27), in case of mis-stratification the actual value is used

Sponsor:	TauRx Therapeutics Ltd.		
Protocol:	TRx-237-039		
Document Version No.:	3.0	Document Date:	07-JUN-2023

- MMSE (16-21, 22-27)
- CDR (0.5, 1 or 2) [binary], in case of mis-stratification the actual value is used
- Age group (<75 years, ≥75 years) [binary]
- Sex (male, female) [binary]
- Race (White, non-White) [binary], Race = White (if checked as only race), otherwise Race = non-White (even if multiple races, including White, were checked)
- Geographic region (North America, Europe) [binary]
- Including the *ApoE* genotype as fixed factor (Presence of the ε4 Allele, Absence of the ε4 Allele) [binary]
- Both HMTM treatment groups pooled versus control

Sensitivity analyses are:

- If more than 5% of the randomized subjects have been mis-stratified, then the primary analyses will be repeated using the actual status at randomization
- Multiple imputation analysis (see Section 4.5.2)

For the two co-primary endpoints and their change from Baseline to Week 52, the empirical distribution functions for HMTM 16 mg/day and control will be compared graphically and using a Kolmogorov-Smirnov test. If the Week 52 visit value is not available, the last available on-treatment value will be used.

Sample SAS code (will be fully validated at the analysis stage):

```
PROC NPAR1WAY DATA=dataset EDF PLOTS=EDFPLOT;
  CLASS treatment;
  VAR scorediff;
  EXACT KS;
  RUN;
```

For the following efficacy endpoint combinations, the correlation of their changes from Baseline to Week 52 will be analyzed (pooling the data from all three treatment groups):

- ADAS-cog11 vs. MRI whole brain volume
- ADCS-ADL23 vs. MRI whole brain volume

Sponsor:	TauRx Therapeutics Ltd.		
Protocol:	TRx-237-039		
Document Version No.:	3.0	Document Date:	07-JUN-2023

If for the respective pairwise comparison, the two Week 52 visit values are not available, the last available on-treatment visit with both respective values being available will be used. A scatter plot will compare the values for the two endpoints and will also present the p-value based on the Pearson correlation.

Sample SAS code (will be fully validated at the analysis stage):

```
PROC CORR DATA=dataset;
  VAR endpoint1 endpoint2;
  RUN;
```

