#### **17.4.5 Handling of Missing and Incomplete Data**

Missing imaging data will not be imputed; it will be assumed that the data are close to missing at random after accounting for the terms in the model for all analyses other than those described for the EMA ITT-based analyses. The EMA ITT-based analyses treat subjects for whom assessments are missing from a certain point onwards as having no treatment benefit thereafter; while the primary analysis assumes that they retained the treatment effect that they had at the point of drop-out, a sensitivity analysis treats them as having lost all treatment effect. While the primary analysis assumes that some of subjects' data might be missing at random for drop-outs, a sensitivity analysis assumes all withdrawals were treatment related. Various other sensitivity analyses, including multiple imputation, time to event, and responder analyses, will be provided to investigate the robustness of the primary and secondary analyses (see respective sections below for more detail; drop-outs are treated as non-responders or having an event of decline in these models).

Efficacy data missing for an entire outcome scale or for the majority of the scale will not be imputed unless stated otherwise. Instead, it will be assumed that the data are close to missing at random after accounting for the terms in the model. However, missing items within a subdomain or scale may be upscaled if some items of the subdomain or scale are present; the SAP will provide details of the handling of partial data for the efficacy endpoints for each scale. As automated data capturing devices are used for all efficacy assessments, the risk of missing data of this type is low. For imaging data, this type of missing data is impossible and consequently they are not subject to upscaling either.

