## **4. STATISTICAL METHODS**

### **4.1. General Methods**

All outputs will be incorporated into Rich Text Format (RTF) files, sorted, and labeled according to the International Council for Harmonisation of Technical Requirements for Pharmaceuticals for Human Use (ICH) recommendations, and formatted to the appropriate page size(s).

Tabulations will be produced for appropriate demographic, Screening, Baseline, efficacy, and safety parameters. For categorical variables, summary tabulations of the number and percentage within each category (with a category for missing data) of the parameter will be presented. For continuous variables, the mean, median, lower quartile (Q1), upper quartile (Q3), standard deviation, minimum and maximum values will be presented. Time-to-event data will be summarized using Kaplan-Meier Methodology using 25th, 50th (median), and 75th percentiles (if available) with associated two-sided 95% confidence intervals (Hall-Wellner Bands), as well as percent of censored observations.

Formal statistical hypothesis testing will be performed on the primary and secondary efficacy endpoints with all tests conducted at the two-sided, 0.05 level of significance.

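### The supplementary Kolmogorov-Smirnov test and plot of Week 52 change should not carry the last on-treatment score forward: this understates decline in subjects without a Week 52 score and can inflate the test when losses differ by arm

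*SAP*

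**What the plan says.** In SAP 5.9.2.1, under the supplementary and other sensitivity analyses, the change from Baseline to Week 52 in ADAS-cog11 and ADCS-ADL23 is examined as a whole distribution: "the empirical distribution functions for HMTM 16 mg/day and control will be compared graphically and using a Kolmogorov-Smirnov test". The rule for a missing endpoint follows: "If the Week 52 visit value is not available, the last available on-treatment value will be used". The sample code has treatment as its only explanatory variable, so nothing adjusts for when the last score was taken.

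The same section correlates each co-primary endpoint with MRI whole brain volume, pooling all three arms. If the two Week 52 values are not available, "the last available on-treatment visit with both respective values being available will be used".

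No significance level is given for the KS test. SAP 4.1 sets the level for the formal primary and secondary tests ("all tests conducted at the two-sided, 0.05 level of significance"), and 0.05 is assumed here.

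Elsewhere the plan handles subjects without a Week 52 score differently:
- Protocol 17.4.5: "Efficacy data missing for an entire outcome scale or for the majority of the scale will not be imputed unless stated otherwise". The data are instead taken to be close to missing at random.
- SAP 5.9.2.1, primary model: an MMRM with no carry-forward.
- SAP 5.9.4: a subject with no Week 52 assessment is a non-responder.
- SAP 5.9.5: a missing scheduled value generally counts as worsening.
- SAP 5.9.1.3 and 5.9.2.2: the while-on-treatment estimand does use a last on-treatment score, but its ANCOVA lists duration of exposure as a covariate.

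**The concern.** The output is described as change to Week 52, but for some subjects it would be change to Week 13, 26 or 39. Because decline is expected throughout the year, the substituted score is on average too good.

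Two consequences follow. The plotted curves are not Week 52 distributions even when the arms lose subjects equally. And if one arm loses more subjects, or loses them earlier, its curve moves further towards less decline with no drug effect at all, so the KS p-value is no longer a 5% test. At stake is a misleading supportive p-value and figure for the co-primary endpoints, not the co-primary result itself.

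**Working it through.** **Inputs (SAP 5.3).** ADCS-ADL23 decline "in the control arm of 7.7 units with an estimated SD of 8.5 units". ADAS-cog11 decline "in the control arm of 6.5 units with an estimated SD of 5.9 units". 200 subjects per arm. Dropout: "These assume a withdrawal rate of 20% to 25% over 52 weeks". No rates by arm are given.

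**The plan's own figures.** With 25% withdrawal, n = 200 × (1 − 0.25) = 150 per arm. The two-sample t-test has noncentrality δ / (σ√(2/n)):
- ADCS-ADL23: 3.4 / (8.5 × √(2/150)) = 3.46, power 93.2% (stated 93.2%).
- ADAS-cog11: 2.6 / (5.9 × √(2/150)) = 3.82, power 96.7% (stated 96.7%).

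So the stated power is matched when a quarter of each arm is counted as not contributing.

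**Decline left out per leaver.** Assume linear decline μ over the year and a last score at fraction t of the year. The omitted decline is μ(1 − t).

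| Last seen | ADAS-cog11 | ADCS-ADL23 |
|---|---|---|
| Week 13 (t = 0.25) | 4.88 | 5.78 |
| Evenly over Weeks 13, 26, 39 (mean t = 0.5) | 3.25 | 3.85 |
| Week 39 (t = 0.75) | 1.62 | 1.93 |

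**Shift in one arm's mean** at 25% dropout, evenly spread: 0.25 × 3.25 = 0.81 and 0.25 × 3.85 = 0.96 units.

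**Spurious difference between arms** at a 15-point gap: 0.15 × 3.25 = 0.49 and 0.15 × 3.85 = 0.58 units, against planned effects of 2.6 and 3.4.

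**KS rejection rate with no drug effect.** Simulated with 200 per arm, 1,500 to 3,000 runs per setting and the asymptotic two-sample KS test at 0.05. Assumptions not in the documents: SD growing with the square root of time to the stated value, autoregressive correlation 0.8 between visits, continuous scores, and dropout unrelated to outcome. Last visits are spread evenly unless stated.

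| Dropout, arm A vs arm B | ADAS-cog11 | ADCS-ADL23 |
|---|---|---|
| 20% vs 20% | 4.7% | 4.5% |
| 25% vs 25% | 5.2% | 5.6% |
| 25% vs 20% | 6.0% | 5.9% |
| 30% vs 20% | 9.3% | 9.0% |
| 30% vs 15% | 14.7% | 11.1% |
| 25% vs 25%, A early, B late | 18.1% | 15.1% |

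In the last row, arm A's leavers are last seen at Weeks 13/26/39 in proportions 0.7/0.2/0.1 and arm B's in 0.1/0.2/0.7. The mean last-seen fractions are 0.35 and 0.65, so the expected shift on ADAS-cog11 is 0.25 × 0.30 × 6.5 = 0.49 units, the same as a 15-point gap in rates.

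A second model with independent quarterly increments gave 6.1%/5.6% at 20% vs 25%, 9.9%/8.0% at 17.5% vs 27.5%, and 15.9%/12.2% at 15% vs 30%. At gaps of 10 points or more, nearly all false rejections favoured the arm with more leavers.

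**Without the carry-forward.** In the first model, KS on observed Week 52 scores alone rejected 4.2–5.8% of the time in every continuous-score setting, including 40% vs 10% dropout.

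**Rounding.** With scores rounded to whole numbers the asymptotic test starts lower (2.2–3.1% at equal dropout), but the pattern remains (30% vs 15%: 8.7%/8.2%). The SAP's sample code requests an exact KS test, so all these rates are approximate for the planned procedure.

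**The case against.** The strongest reply is about weight. The KS comparison is supplementary and plays no part in the co-primary decision. The plan already has an MMRM without carry-forward, multiple imputation, a completers analysis, a responder analysis and a time-to-decline analysis. A last-on-treatment outcome is also a defined secondary estimand. Subjects who stop drug are encouraged to stay for assessments, and the Week 52 analysis window for the scales runs from Day 320 to Day 456, so carry-forward may apply to fewer subjects than withdraw. All of this stands and limits the point to an improvement. It does not justify labelling the result as change to Week 52.

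A reader might also infer more than the documents support:
- *That observed off-treatment Week 52 scores are overwritten.* The rule applies only when no Week 52 value is available.
- *That a 12–15% error rate is to be expected, or that the bias favours HMTM.* No rates by arm are given. If the arms differ only across the planned 20–25% range, the rate is about 6%, and the direction depends on which arm loses more subjects or loses them earlier.
- *That the SAP contradicts the protocol.* Protocol 17.4.5 allows exceptions that are stated, and the protocol describes no KS test. The change log's removal of a carry-forward analysis concerns superseded text.
- *That worst-rank coding of leavers would repair the test.* It turns a dropout gap directly into KS distance. The 5% critical distance at 200 per arm is about 1.358 × √(2/200) = 0.136, so a 15-point gap alone exceeds it. Simulated null rejection was about 13% at 20% vs 25%, 42–44% at 17.5% vs 27.5%, and 81–83% at 15% vs 30%.
- *That these error rates apply to the correlations.* Those pool all arms and use paired values from the same visit. The only issue there is mixing changes over different lengths of follow-up.

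**Conclusion.** The point holds as a modest one. As specified, the figure and test do not describe Week 52 change. Under linear decline and evenly spread last visits, each leaver's decline is understated by about 3.25 ADAS-cog11 and 3.85 ADCS-ADL23 units, and an arm's mean by about 0.8 and 1.0 units at 25% dropout.

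The KS test keeps roughly its 5% level when rates and timing match between arms. It rises to about 6% at 20% vs 25%, 8–10% at a 10-point gap, 12–15% at a 15-point gap, and 15–18% at equal 25% dropout with opposite timing. These figures rest on assumed gaps between arms and on dropout unrelated to outcome, so the inflation in this trial cannot be stated from the documents.

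**What to change.** Remove the carry-forward from the KS test and plot and run both on observed Week 52 change. Repeat them on multiply imputed Week 52 values from SAP 4.5.2, naming the imputation model, since the MITT version omits treatment and the version in 4.5.2.2 includes it. KS p-values do not pool by Rubin's rules, so show the averaged distribution function and the spread of p-values over the 50 datasets. Report the p-value as supportive only, and do not use worst-rank coding for the test.

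If a last-on-treatment version is kept, label it as that. State whether a Week 52 score excluded because of AChEI or memantine use counts as unavailable. For the correlations with whole brain volume, use observed Week 52 pairs.

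The cost is SAP wording, one derivation and a rerun on existing imputed data. The observed-only version has fewer subjects and is itself biased if dropout depends on outcome, which is why the imputed version should accompany it. Because SAP v3.0 follows partial unblinding (SAP section 10), identify the change as post hoc and show both versions.
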